#### **7.4.2. Systemic Embolism**

Systemic embolism will be judged to occur where there is a clinical history consistent with an acute loss of blood flow to a peripheral artery (or arteries), which is supported by evidence of embolism from surgical specimens, autopsy, angiography, or other objective testing.

#### **7.4.3. Major Bleeding**

Clinically overt bleeding is defined as new onset, visible bleeding or signs or symptoms suggestive of bleeding with confirmatory imaging techniques which can detect the presence of blood (eg, ultrasound (US), CT, MRI).

The definition of major bleeding described below is adapted from the International Society on Thrombosis and Hemostasis (ISTH) definition.

Major bleeding is defined as clinically overt bleeding that is accompanied by one or more of the following:

- A decrease in hemoglobin (Hgb) of 2 g/dL or more
- A transfusion of 2 or more units of packed red blood cells
- Bleeding that occurs in at least one of the following critical sites:
  - Intracranial.
  - Intra-spinal.
  - Intraocular (within the corpus of the eye; thus, a conjunctival bleed is not an intraocular bleed).
  - Pericardial.
  - Intra-articular.
  - Intramuscular with compartment syndrome.
  - Retroperitoneal.
- Bleeding that is fatal.

#### **7.4.4. Clinically Relevant Non-Major Bleeding**

The definition of clinically relevant non-major bleeding will be clinically overt bleeding that consists of:

- Any bleeding compromising hemodynamics.
- Any bleeding leading to hospitalization.
- Subcutaneous hematoma larger than 25 cm^2, or 100 cm^2 if there was a traumatic cause.
- Intramuscular hematoma documented by ultrasonography.
- Epistaxis that lasted for more than 5 minutes, was repetitive (ie, two or more episodes of bleeding more extensive than spots on a handkerchief within 24 hours), or led to an intervention (eg, packing or electrocoagulation).
- Gingival bleeding occurring spontaneously (ie, unrelated to eating or tooth brushing) or lasting for more than 5 minutes.
- Hematuria that was macroscopic and was spontaneous or lasted for more than 24 hours after instrumentation (eg, catheter placement or surgery) of the urogenital tract.
- Macroscopic gastrointestinal hemorrhage, including at least one episode of melena or hematemesis, if clinically apparent with positive results on a fecal occult-blood test.
- Rectal blood loss, if more than a few spots on toilet paper.
- Hemoptysis, if more than a few speckles in the sputum and not occurring within the context of pulmonary embolism or:
  - Any other bleeding type considered to have clinical consequences for a subject, such as medical intervention, the need for unscheduled contact (visit or telephone call) with a physician, or temporary cessation of a study drug; or
  - Associated with pain or impairment of activities of daily life.

#### **7.5. Details of Cardioversion**

The date and time of all attempted cardioversion procedures and rhythm status according to ECG analysis will be captured within the CRF at Visit 2 and Visit 3. The performance of ECG monitoring is in accordance with the investigator's usual practice, and it is expected this would be performed pre and post cardioversion procedures at appropriate times.

Attempts are defined as the number of times the subject is admitted for the cardioversion procedure and not the number of attempts during a single admission.

## **7.6. Length of In-Hospital Stay**

Length of in-hospital stay is defined as the number of hours from hospital admission to hospital discharge following early cardioversion.

The date and time of all hospital admissions and discharges following cardioversion will be captured within the CRF at Visit 2 and 3.

## **7.7. Collection of Local Clinical Laboratory Parameters**

Local clinical laboratory assessments should be performed as part of the routine care for subjects undergoing cardioversion at the clinical practice.

From these routine assessments hemoglobin and serum creatinine will be recorded within the CRF from Visit 1 to Visit 3.

## **8. ADVERSE EVENTS**

In this clinical protocol adverse and serious adverse event reporting will be managed according to the following BMS standard operating definitions and procedures.

An *Adverse Event (AE)* is defined as any new untoward medical occurrence or worsening of a preexisting medical condition in a clinical investigation subject administered study drug and that does not necessarily have a causal relationship with this treatment. An AE can therefore be any unfavorable and unintended sign (such as an abnormal laboratory finding), symptom, or disease temporally associated with the use of study drug, whether or not considered related to the study drug.

The causal relationship to study drug is determined by a physician and should be used to assess all adverse events (AE). The causal relationship can be one of the following:

- Related: There is a reasonable causal relationship between study drug administration and the AE.
- Not related: There is not a reasonable causal relationship between study drug administration and the AE.

The term "reasonable causal relationship" means there is evidence to suggest a causal relationship.

Adverse events can be spontaneously reported or elicited during open-ended questioning, examination, or evaluation of a subject. (In order to prevent reporting bias, subjects should not be questioned regarding the specific occurrence of one or more AEs).

BMS will be reporting adverse events to regulatory authorities and ethics committees according to local applicable laws including European Directive 2001/20/EC and Food and Drug Administration (FDA) Code of Federal Regulations 21 CFR Parts 312 and 320.

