#### **5.2.4. Compliance**

For subjects randomized to apixaban, compliance based on study drug tablet count will be recorded both at the time of cardioversion (Visit 2) and at Visit 3 for all subjects.

For subjects randomized to usual care, compliance is confirmed by ongoing INR monitoring. In addition, tablet count should be recorded both at the time of cardioversion (Visit 2) and at Visit 3 for all subjects where usual care has been dispensed directly by the site.

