### 6.2. Visit 2 Cardioversion

The Investigator or designee will:

- Assess and record clinical endpoints (stroke, systemic embolism, major bleeding, clinically relevant non-major bleeding, and all cause death) and whether they meet the serious adverse event reporting criteria.
- Perform study drug treatment compliance check, see [Section 5.2.4](#).
- Assess and record local clinical laboratory parameters, including INR for VKA-treated subjects.
- Assess and record cardioversion details (timing, type, attempts, and rhythm status), and use of image guidance (eg, TEE/TOE or CT).
- Assess and record adverse events.
- Collect and dispense study drug treatment, if required, as per label and routine clinical practice, and visually confirm the subject has received their medicine supply, see [Section 5.2.2](#).

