### 6.3. Visit 3 (30 days (±7) Post Cardioversion or 90 days (±7) Following Enrollment Visit 1 if Cardioversion is not Performed). See [Figure 2](#) for Further Examples of Timing of Visit 3.

The Investigator or designee will:

- Assess and record local clinical laboratory parameters, including INR for VKA-treated subjects.

- Assess and record ECG details
- Assess and record clinical endpoints (stroke, systemic embolism, major bleeding, clinically relevant non-major bleeding and all cause death) and whether they meet the serious adverse event reporting criteria.
- Record length of in-hospital stay.
- Assess and record adverse events.
- Collect study drug treatment.
- Perform study drug treatment compliance check, see [Section 5.2.4](#).

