### **7.4. Clinical Endpoints**

Clinical endpoints will be assessed by the Investigator to determine whether they meet the protocol criteria as described below. Clinical events meeting the criteria will be recorded on the CRF and independently adjudicated.

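### The protocol does not say whether its rule against asking about specific adverse events covers the bleeding endpoints, and it gives no common method for eliciting them

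*Protocol*

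**What the plan says.** Section 8 of the protocol defines an adverse event as "any new untoward medical occurrence or worsening of a preexisting medical condition" in a subject given study drug. On how such events are found, it says "Adverse events can be spontaneously reported or elicited during open-ended questioning, examination, or evaluation of a subject", and then, to prevent reporting bias, that "subjects should not be questioned regarding the specific occurrence of one or more AEs". It makes no exception for clinical endpoints.

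Section 6.2 gives the Visit 2 duty: "Assess and record clinical endpoints (stroke, systemic embolism, major bleeding, clinically relevant non-major bleeding, and all cause death". Section 6.3 repeats it at Visit 3 and, like 6.2, ties endpoints to safety reporting: "clinically relevant non-major bleeding and all cause death) and whether they meet the serious adverse event reporting criteria". Section 7.4 says who decides: "Clinical endpoints will be assessed by the Investigator to determine whether they meet the protocol criteria as described below". None of these sections says how the information is to be obtained from the subject.

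Section 7.4.4 lists the CRNM criteria. Some rest mainly on what the subject recalls, for example "Epistaxis that lasted for more than 5 minutes", spontaneous gum bleeding, and rectal blood loss beyond spotting.

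On monitoring, Section 5.2.4 says "For subjects randomized to usual care, compliance is confirmed by ongoing INR monitoring", whereas apixaban compliance rests on tablet counts at Visits 2 and 3. Section 5.2.3.1 leaves INR frequency to the investigator's usual practice. Section 3 makes the trial open label. Section 9.4 provides adjudication blinded to treatment.

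**The concern.** A bleed is both an adverse event and a clinical endpoint. One rule discourages a direct question about it and another requires it to be assessed. A site that follows Section 8 closely may ask only how the subject has been. A site that follows 6.2 and 6.3 closely may ask about nosebleeds, gums and stools. Both could cite the protocol.

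A minor bleed is easily left out of an answer to an open question, particularly at Visit 3, which falls 30 days after cardioversion, or 90 days after enrolment if there is none. If elicitation is unstructured, capture depends on local habit and on how often the subject speaks to someone who records bleeds. In an open-label trial where one arm has ongoing INR monitoring, neither need be equal between arms.

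At stake are the CRNM comparison and the composite of major and CRNM bleeding. SAP Section 8.2.4 reports exact risk ratios with p-values for the clinical endpoints and a Kaplan-Meier display for that composite.

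**Working it through.** **1. The plan's own bleeding figure.** Section 9.1 predicts major bleeding of about 0.45%, as 2 events on apixaban and 5 on usual care. Check: (2 + 5)/1500 = 0.467%, and 0.0045 × 1500 = 6.75, about 7 events. The figure reproduces. It concerns major bleeding only, so this point does not disturb it. The plan gives no CRNM prediction and no power calculation.

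**2. Are the two instructions reconciled?**
- A bleed on study drug falls within the Section 8 definition of an adverse event.
- Section 8 has no exemption for endpoints. Section 8.1 discusses endpoint components within the same adverse event chapter, and Section 2 speaks of serious adverse events handled as endpoints, so the two categories overlap.
- Against this, endpoints have their own row in the Schedule of Activities, their own bullet at each visit and their own section (7.4).

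The text supports either reading and nothing settles it.

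**3. Which endpoints are exposed?**
- Major bleeding (7.4.3) turns on haemoglobin fall, transfusion, critical site or death. Haemoglobin is recorded in both arms from Visit 1 to Visit 3 (7.7). Not exposed.
- CRNM items shown by ultrasound, haemodynamic compromise or hospitalization (7.4.4): not exposed.
- CRNM items known mainly from history (nosebleed duration, spontaneous gum bleeding, rectal blood loss): exposed. They pass into the CRNM total and the major/CRNM composite.

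**4. Can adjudication repair it?** Under 7.4, events judged to meet the criteria are recorded and then adjudicated. A bleed that was never mentioned never reaches the adjudicator.

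**5. What could unequal capture do?** The documents give no capture rates, so every rate here is assumed.

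Observed risk ratio = true risk ratio × (apixaban capture ÷ usual-care capture).

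The third column takes a true ratio of 4.07/6.01 = 0.68, from the major or CRNM bleeding rates that Section 1.2 cites for the earlier apixaban-versus-warfarin trial.

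| Apixaban capture | Usual-care capture | Observed if true 1.00 | Observed if true 0.68 |
|---|---|---|---|
| 90% | 90% | 1.00 | 0.68 |
| 80% | 90% | 0.89 | 0.60 |
| 70% | 90% | 0.78 | 0.53 |
| 60% | 90% | 0.67 | 0.45 |
| 50% | 90% | 0.56 | 0.38 |
| 90% | 70% | 1.29 | 0.87 |

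The table applies capture to every event counted. If only a share h of events depends on the subject's account (the same h in both arms) and the rest are always found, the multiplier becomes [(1 − h) + h × apixaban capture] ÷ [(1 − h) + h × usual-care capture]. This equals the table at h = 1 and is 1 at h = 0. For the whole CRNM endpoint or the composite, the distortion is therefore smaller than shown. The documents do not give h.

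**6. How many events are involved?** At the cited annual rates of 4.07% and 6.01%, with 750 per arm:
- 30 days: 750 × 0.0407 × 30/365 = 2.5 on apixaban; 750 × 0.0601 × 30/365 = 3.7 on usual care.
- 90 days: 7.5 and 11.1 by the same formula.

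The cited population differs from this one. If counts are of this order, a few missed bleeds would visibly move the ratio.

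**The case against.** The strongest reply is that there is no ban on asking about endpoints. The sentence sits in the adverse event section and speaks of adverse events, whereas endpoints have a separate track. A specific duty to assess named bleeding endpoints is naturally read as leave to ask about them. This largely stands: a reader might infer that Section 8 prohibits endpoint questions, and the documents do not support that. What remains is that they do not say otherwise, and they give no method.

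Section 8 also allows open-ended questioning, examination and evaluation, so ascertainment does not rest on spontaneous reports alone. Once a nosebleed is mentioned, asking how long it lasted is follow-up of a reported event. That stands too, but it does not help with a bleed that is never mentioned.

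A reader might further infer that routine INR checks create CRNM events, because Section 7.4.4 counts a bleed that requires unscheduled contact with a physician. They do not: the bleed must create the need, and a routine check is neither unscheduled nor prompted by a bleed.

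Unequal contact is an inference. Study visits are identical in both arms, INR frequency is not fixed, and nothing says that whoever takes the INR sample asks about bleeding. Closer scrutiny of the newer drug could push the other way.

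Finally, the study is descriptive with no hypothesis test, and the CRF and Adjudication Charter are not among the documents, so a standard bleeding prompt may exist. This limits the weight of the point, but a prompt in the CRF would still sit beside an unreconciled protocol sentence.

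**Conclusion.** The point holds as an unreconciled instruction with no common elicitation method. It bears on the history-based CRNM items and, through them, on the major/CRNM composite. It does not bear on major bleeding, on the objectively shown CRNM items, or on any sample size figure.

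A reader might infer that CRNM bleeding is under-counted more on apixaban, so that the comparison favours apixaban. The documents do not show this. Unequal capture is plausible, given open-label treatment and INR monitoring specified only for usual care, but neither its existence nor its direction is documented. The 0.56 to 1.29 range for a true ratio of 1.00 rests wholly on assumed capture between 50% and 90%, applied to all events. It shows sensitivity and is not an estimate of bias.

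No decision rule depends on this. It is a modest, inexpensive improvement that protects the interpretation of a reported comparison likely to rest on few events.

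**What to change.** - In Section 8, add one sentence stating that the restriction on questioning does not apply to the clinical endpoints of Section 7.4.
- In 6.2 and 6.3, require the same short scripted endpoint questions, built from the 7.4 criteria, for every subject in both arms at Visits 2 and 3. An identical script also serves Section 8's own aim of avoiding reporting bias.
- Optionally, record on the CRF whether each bleed was first reported at a scheduled visit or at another contact, and tabulate this by arm. That would let the reader see whether capture routes differed.

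Cost: a protocol clarification, a short form at visits that already take place and, if the option is taken, one CRF field and one table. CRNM counts would probably rise slightly in both arms. No visit, treatment rule or sample size changes.

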### 8.1. Serious Adverse Events

A *Serious Adverse Event (SAE)* is any untoward medical occurrence that at any dose:

- results in death;
- is life-threatening (defined as an event in which the subject was at risk of death at the time of the event; it does not refer to an event which hypothetically might have caused death if it were more severe);
- requires inpatient hospitalization or causes prolongation of existing hospitalization (see **NOTE**);
- results in persistent or significant disability/incapacity;
- is a congenital anomaly/birth defect;
- is an important medical event (defined as a medical event(s) that may not be immediately life-threatening or result in death or hospitalization but, based upon appropriate medical and scientific judgment, may jeopardize the subject or may require intervention [eg, medical, surgical] to prevent one of the other serious outcomes listed in the definition above). Examples of such events include, but are not limited to, intensive treatment in an emergency room or at home for allergic bronchospasm; blood dyscrasias or convulsions that do not result in hospitalization). Potential drug induced liver injury (DILI) is also considered an important medical event. (See [Section 8.6](#) for the definition of potential DILI).

Suspected transmission of an infectious agent (eg, pathogenic or nonpathogenic) via the study drug is an SAE.

Although pregnancy, overdose, cancer, and potential drug induced liver injury (DILI) are not always serious by regulatory definition, these events must be handled as SAEs. (See [Section 8.1.1](#) for reporting pregnancies).

Any component of a study endpoint that is considered related to study therapy (eg, death is an endpoint; if death occurred due to anaphylaxis, anaphylaxis must be reported) should be reported as an SAE (see [Section 8.1.1](#) for reporting details).

#### **NOTE:**

The following hospitalizations are not considered SAEs in BMS clinical studies:

- a visit to the emergency room or other hospital department <24 hours, that does not result in admission (unless considered an important medical or life-threatening event);
- elective surgery, planned prior to signing consent;
- admissions as per protocol for a planned medical/surgical procedure;

- routine health assessment requiring admission for baseline/trending of health status (eg, routine colonoscopy);
- medical/surgical admission other than to remedy ill health and planned prior to entry into the study. Appropriate documentation is required in these cases;
- admission encountered for another life circumstance that carries no bearing on health status and requires no medical/surgical intervention (eg, lack of housing, economic inadequacy, caregiver respite, family circumstances, administrative reason).

### **8.1.1. Serious Adverse Event Collection and Reporting**

Sections 5.6.1 and 5.6.2 in the Investigator Brochure (IB) represent the Reference Safety Information to determine expectedness of serious adverse events for expedited reporting.

Following the subject's written consent to participate in the study, all SAEs, whether related or not related to study drug, must be collected, including those thought to be associated with protocol-specified procedures. All SAEs must be collected that occur during the screening period and within 30 days of discontinuation of dosing.

The investigator should report any SAE that occurs after these time periods and that is believed to be related to study drug or protocol-specified procedure.

An SAE report must be completed for any event where doubt exists regarding its seriousness.

If the investigator believes that an SAE is not related to study drug, but is potentially related to the conditions of the study (such as withdrawal of previous therapy or a complication of a study procedure), the relationship must be specified in the narrative section of the SAE Report Form.

SAEs, whether related or not related to study drug, and pregnancies must be reported to BMS (or designee) within 24 hours of awareness of the event. SAEs must be recorded on the SAE Report Form; pregnancies on a Pregnancy Surveillance Form (electronic or paper forms). The preferred method for SAE data reporting collection is through the electronic case report form (eCRF). The paper SAE/pregnancy surveillance forms are only intended as a back-up option when the eCRF system is not functioning. In this case, the paper forms are to be transmitted via email or confirmed facsimile (fax) transmission to:

**SAE Email Address:** Refer to [Contact Information list](#).

**SAE Facsimile Number:** Refer to Contact Information list.

For studies capturing SAEs through electronic data capture (EDC), electronic submission is the required method for reporting. In the event the electronic system is unavailable for transmission, paper forms must be used and submitted immediately. When paper forms are used, the original paper forms are to remain on site.

**SAE Telephone Contact** (required for SAE and pregnancy reporting): Refer to Contact Information list.

If only limited information is initially available, follow-up reports are required. (Note: Follow-up SAE reports must include the same investigator term(s) initially reported).

If an ongoing SAE changes in its intensity or relationship to study drug or if new information becomes available, the SAE report must be updated and submitted within 24 hours to the BMS (or designee) using the same procedure used for transmitting the initial SAE report.

All SAEs should be followed to resolution or stabilization.

## **8.2. Nonserious Adverse Events**

A *nonserious adverse event* is an AE not classified as serious.

### **8.2.1. Nonserious Adverse Event Collection and Reporting**

The collection of nonserious AE information should begin at initiation of study drug. Nonserious AE information should also be collected from the start of a placebo lead-in period or other observational period intended to establish a baseline status for the subjects.

Nonserious AEs should be followed to resolution or stabilization, or reported as SAEs if they become serious (see [Section 8.1.1](#)). Follow-up is also required for nonserious AEs that cause interruption or discontinuation of study drug and for those present at the end of study treatment as appropriate. All identified nonserious AEs must be recorded and described on the nonserious AE page of the CRF (paper or electronic).

Completion of supplemental CRFs may be requested for AEs and/or laboratory abnormalities that are reported/identified during the course of the study.

